#### **4.4 Lifestyle Considerations**

Not applicable.

#### **4.5 Screen Failures**

Individuals who do not meet the criteria for participation in this trial (screen failure) because of a use of a disqualifying medication may be rescreened after the required period of not using that medication. Rescreened participants will be assigned the same participant number as for the initial screening.

## 4.6 Strategies for Recruitment and Retention

### 5. Registration Procedures

#### 5.1 Subject Registration (WCM only)

Subjects will be registered within the WRG-CT as per the standard operating procedure for Subject Registration.

#### 5.2 Subject Registration (Sub-sites)

Not applicable.

### 6. Study Procedures

#### 6.1 Schedule of Assessments

Visit Number: 1 2 3 4 5 6 7 8 9 10 11

|                                    | Pre-Study | Day 0 | Wk 2 | Wk 4 | Wk 6 | Wk 8 | Wk 10 | Wk 12 | Wk 14 | Wk 16 | Wk 18 | Wk 20 |
|------------------------------------|-----------|-------|------|------|------|------|-------|-------|-------|-------|-------|-------|
| Informed consent                   | X         |       |      |      |      |      |       |       |       |       |       |       |
| Evaluation for Entry               | X         |       |      |      |      |      |       |       |       |       |       |       |
| Demographics                       | X         |       |      |      |      |      |       |       |       |       |       |       |
| Medication History                 | X         | X     | X    | X    | X    | X    | X     | X     | X     | X     | X     | X     |
| Medical History*                   | X         | X     | X    | X    | X    | X    | X     | X     | X     | X     | X     | X     |
| Height                             | X         |       |      |      |      |      |       |       |       |       |       |       |
| Weight                             | X         |       |      |      |      |      |       |       |       |       |       |       |
| Vital Signs                        | X         |       |      |      |      |      |       |       |       |       |       |       |
| Skin Exam + Photos*                | X         | X     | X    | X    | X    | X    | X     | X     | X     | X     | X     | X     |
| PASI Score                         | X         | X     | X    | X    | X    | X    | X     | X     | X     | X     | X     | X     |
| IGA Score                          | X         | X     | X    | X    | X    | X    | X     | X     | X     | X     | X     | X     |
| DLQI Score                         | X         | X     | X    | X    | X    | X    | X     | X     | X     | X     | X     | X     |
| Itch Score                         | X         | X     | X    | X    | X    | X    | X     | X     | X     | X     | X     | X     |
| Urine pregnancy test               | X         | X     | X    | X    | X    | X    | X     | X     | X     | X     | X     | X     |
| CMP, CBC w/Diff,                   | X         |       |      |      |      |      |       |       |       | X     |       |       |
| T Cell FACS, Biopsy of Skin Lesion |           | X     |      |      |      |      |       |       |       |       |       |       |
| HIV Serology, HbA1c                | X         |       |      |      |      |      |       |       |       |       |       |       |

|                         |   |   |   |   |   |   |   |   |   |   |   |   |   |  |
|-------------------------|---|---|---|---|---|---|---|---|---|---|---|---|---|--|
| Assess Adverse Event    |   | X | X | X | X | X | X | X | X | X | X | X | X |  |
| ECG                     | X |   |   | X |   | X |   | X |   | X |   | X |   |  |
| Randomization           | X |   |   |   |   |   |   |   |   |   |   |   |   |  |
| Medication Dispensation |   | X |   |   |   | X |   |   |   |   |   |   |   |  |
| Pill Counts             |   |   | X | X | X | X | X | X | X | X |   |   |   |  |

**All visits have a +/- 2-day window. Each visit is first day of the week indicated.**

#### Schedule of Visits in Extension Phase

| Visit Number            | 11/12* | 13   | 14   | 15    |
|-------------------------|--------|------|------|-------|
|                         | Day 1  | Wk 4 | Wk 8 | Wk 12 |
| Informed consent        | X      |      |      |       |
| Evaluation for Entry    | X      |      |      |       |
| Medication History      | X      | X    | X    | X     |
| Medical History**       | X      | X    | X    | X     |
| Skin Exam + Photos**    | X      | X    | X    | X     |
| PASI Score              | X      | X    | X    | X     |
| IGA Score               | X      | X    | X    | X     |
| DLQI Score              | X      | X    | X    | X     |
| Itch Score              | X      | X    | X    | X     |
| Urine pregnancy test    | X      | X    | X    | X     |
| Assess Adverse Event    | X      | X    | X    | X     |
| ECG                     | X      | X    | X    | X     |
| Medication Dispensation | X      |      | X    |       |
| Pill Counts             |        | X    | X    | X     |

**All visits have a +/- 2-day window. Each visit is first day of the week indicated.**

\*Subjects enrolling in extension prior to visit 11 can combine visit 11 and 12.

\*\*Skin Exam: The entire glabrous skin surface will be examined.

\*\*Photography: Photographs will be taken to demonstrate the extent and morphology of lesions of psoriasis.

\*\*Medical History: Characteristics of the patient's psoriasis will be obtained (duration, areas of involvement, past therapies and degree of itch). History of active medical problems, any immunosuppressive disorders will be queried. Family history of psoriasis or other inflammatory skin diseases will also be obtained.

#### **6.1.1 Screening Visit (2-10 days before start of treatment)**

- Informed consent
- Demographics
- Medication history
- Medical history
- Skin exam + photos
- PASI Score
- IGA Score
- DLQI Score
- Itch Score
- Beta-HCG
- HIV Serology
- CBC w/Diff, CMP, Hemoglobin A1c
- ECG

#### **6.1.2 Treatment Phase**

Eligible subjects will be randomly assigned to rimegepant or placebo treatment groups in a 1:1 ratio using a stratified permuted block randomization scheme developed by the data manager/study statistician.

##### **6.1.2.1 Visit 1 (baseline; Day 0)**

- Medication history (changes)
- Medical history (changes)
- Skin exam + photos
- PASI score
- IGA Score
- DLQI Score
- Itch Score
- Adverse Events Assessment
- Concomitant medication

##### **6.1.2.2 Visits 2-12 ( $\pm$ 2 day(s))**

- Medication history (changes)
- Medical history (changes)
- Skin exam + photos
- PASI score
- IGA Score
- DLQI Score

- Itch Score
- Adverse Events Assessment
- Concomitant medication
- ECGs will be obtained on Visits 3,5,7 and 9.

### **6.1.3 Follow-up Phase**

Visits 11 and 12 are follow-ups after completion of the treatment phase

#### **Extension Phase**

Visits 13-15 have the same assessments as visits 2-12 except they will have a frequency of every 4 weeks.

## **7. Study Intervention**

### **7.1 Study Intervention/Device Description**

In this protocol, the investigational product will come in 2 forms either tablet or ODTs. Both active forms of tablets and ODTs will have 75mg of rimegepant and both formulations provide bioequivalent exposures, thus support equivalent PK performance. The tablets will be provided in 30 count HDPE bottles and labeled in a double-blind fashion that is identical to placebo tablets. The ODTs are packaged into multi-laminated blisters sealed with a foil backing and labeled in a double-blind fashion that is identical to placebo ODTs. Because the blister packs are in units of 8, 32 ODTs of rimegepant or placebo will be distributed. Any leftover investigational product will be returned to the study team during visits 5, 9 and if applicable, extension visit 14.

The investigational product will be shipped to the pharmacy by Pfizer Inc. and should be stored in a secure area according to local regulations. It is the responsibility of the investigator to ensure that investigational product is only dispensed to study subjects. The investigational product must be dispensed only from official study sites by authorized personnel according to local regulations.

### **7.2 Availability**

The full amount of Rimegepant and placebo will be supplied by Pfizer, Inc. and shipped to the site pharmacy prior to the initiation of the trial. If additional product is required, contact the sponsor directly.

### **7.3 Acquisition and Accountability**

Agent Inventory Records/Device Logs – The investigator, or a responsible party designated by the investigator, will maintain a careful record of the inventory and disposition of all agents/device received from *Sponsor* on a Drug Accountability Record Form (DARF) or Device Log.

#### **7.4 Formulation, Appearance, Packaging, and Labeling**

The rimegepant active and placebo tablets are packaged in 30 count HDPE bottles and will have a blinded label which will include a unique bottle number, the product name, labeling lot number, storage conditions and dosing directions. The unique bottle number is linked to the treatment arm in a blinded fashion. The rimegepant active and placebo ODTs are packaged in 8-count multi-laminated blisters backed with foil and will be labeled similarly to the tablet bottles.

#### **7.5 Product Storage and Stability**

The investigational product should be stored at room temperature according to conditions on the clinical label in a secure area according to local regulations.

It is the responsibility of the investigator to ensure that investigational product is only dispensed to study subjects. The investigational product must be dispensed only from official study sites by authorized personnel according to local regulations.

If concerns regarding the quality or appearance of the study drug arise, do not dispense the study drug and contact the sponsor immediately.

#### **7.6 Preparation**

The investigational product will be assigned by the unblinded pharmacist after patient randomization through use of the unique bottle numbers. The pharmacist will add the appropriate subject number on the bottle label and provide it to the site staff for dispensation to the subject.

#### **7.7 Dosing and Administration**

Each subject will take a 75-mg tablet/ODT of rimegepant orally or a matching placebo tablet/ODT orally every other day for 16 weeks. Subjects will receive 30 tablets or 32 ODTs of rimegepant or matching placebo in each bottle or four 8-count blister packs at the initial visit after the subject is randomized. The subject will be instructed to dose around the same time every other day. The subject must bring the bottle/blister packs back for each visit for drug accountability. A second 30 tablet or 32 ODT supply will be dispensed at week 8. Pill counts will be performed at each visit to assess compliance.

##### **7.7.1 Dosing Delays/Dose Modifications**

For any serious adverse effects, dosing will be immediately discontinued and appropriate care provided. Some nausea is expected.

#### **7.8 General Concomitant Medication and Supportive Care Guidelines**

Concomitant administration of rimegepant with strong inhibitors of CYP3A4 results in a significant increase in rimegepant exposure.

**CYP3A4 Inhibitors (Strong) Interacting Members:** Atazanavir, Ceritinib, Clarithromycin, Cobicistat, Darunavir, Idelalisib, Indinavir, Itraconazole, Ketoconazole (Systemic), Lopinavir, MiFEPRIStone, Nefazodone, Nelfinavir, Omibitasvir, Paritaprevir,

and Ritonavir, Omritasvir, Paritaprevir, Ritonavir, and Dasabuvir, Posaconazole, Ritonavir, Saquinavir, Telithromycin, Tucatinib, Voriconazole

Concomitant administration of rimegepant with moderate inhibitors of CYP3A4 may result in increased exposure of rimegepant.

- **CYP3A4 Inhibitors (Moderate) Interacting Members:** Aprepitant, Conivaptan, Crizotinib, Diltiazem, Dronedarone, Duvelisib, Erythromycin (Systemic), Fedratinib, Fluconazole, Fosamprenavir, Fosnetupitant, Grapefruit Juice, Imatinib, Isavuconazonium Sulfate, Lefamulin, Letermovir, Netupitant, Nilotinib, Ribociclib, Schisandra, Verapamil

Concomitant administration of rimegepant with strong or moderate inducers of CYP3A can result in a significant reduction in rimegepant exposure, which may lead to loss of efficacy.

- **CYP3A4 Inducers (Strong) Interacting Members:** Apalutamide, CarBAMazepine, Enzalutamide, Fosphenytoin, Lumacaftor and Ivacaftor, Mitotane, PHENobarbital, Phenytoin, Primidone, RifAMPin
- **CYP3A4 Inducers (Moderate) Interacting Members:** Bexarotene (Systemic), Bosentan, Cenobamate, Dabrafenib, Efavirenz, Eslicarbazepine, Etravirine, Lorlatinib, Modafinil, Nafcillin, Pexidartinib, Rifabutin, Rifapentine, St John's Wort

Rimegepant is a substrate of permeability glycoprotein (P-gp) and Breast Cancer Resistance Protein (BCRP) efflux transporters. Concomitant administration of rimegepant with inhibitors of P-gp or BCRP may result in a significant increase in rimegepant exposure.

- **BCRP/ABCG2 Inhibitors Interacting Members:** Atazanavir, Capmatinib, Clopidogrel, Cobicistat, CycloSPORINE (Systemic), Daclatasvir, Darolutamide, Dasabuvir, Elbasvir, Eltrombopag, Eluxadoline, Fostamatinib, Fostemsavir, Glecaprevir and Pibrentasvir, Grazoprevir, Lapatinib, Ledipasvir, Leflunomide, Lopinavir, Omritasvir, Paritaprevir, and Ritonavir, Omritasvir, Paritaprevir, Ritonavir, and Dasabuvir, Osimertinib, Regorafenib, Rolapitant, Simeprevir, Tedizolid, Teriflunomide, Velpatasvir, Voxelaprevir
- **P-glycoprotein/ABCB1 Inhibitors Interacting Members:** Amiodarone, Azithromycin (Systemic), Capmatinib, Carvedilol, CycloSPORINE (Systemic), Daclatasvir, Dronedarone, Elagolix, Elagolix, Estradiol, and Norethindrone, Elexacaftor, Tezacaftor, and Ivacaftor, Eliglustat, Erythromycin (Systemic), Flibanserin, Fostamatinib, Glecaprevir and Pibrentasvir, Ivacaftor, Lapatinib, Ledipasvir, Neratinib, Osimertinib, Propafenone, QuiNIDine, QuiNINE, Ranolazine, Rolapitant, Simeprevir, Tezacaftor and Ivacaftor, Tucatinib, Velpatasvir, Vemurafenib, Verapamil

**Exceptions** Clarithromycin, Itraconazole, Ketoconazole (Systemic), Omritasvir, Paritaprevir, and Ritonavir, Ritonavir

**Potential subjects on any medication that is a strong or moderate inhibitor of CYP3A, a strong or moderate inducer of CYP3A or an inhibitor of p-gp or BCRP will be excluded from participation in the study.**

All concomitant medications will be recorded and/or updated on subject medication log throughout the course of the study and saved in subject binder, if applicable.

### **7.9 Duration of Therapy and Criteria for Removal from Study**

In the absence of treatment delays due to adverse event(s), treatment will continue for 16 weeks or until one of the following criteria applies:

- Disease progression requiring intervention,
- Intercurrent illness that prevents further administration of treatment,
- Unacceptable adverse event(s),
- Subject decides to withdraw from the study,
- Initiation of prohibited medication, or
- General or specific changes in the subject's condition render the subject unacceptable for further treatment in the judgment of the investigator.

### **7.10 Duration of Follow Up**

Subjects will be followed for 4 weeks after discontinuation of the investigative pharmaceutical agent. Subjects removed from study for unacceptable adverse events will be followed until resolution or stabilization of the adverse event.

### **7.11 Measures to Minimize Bias: Randomization and Blinding**

#### Screening and Registration into the Study Database

Once informed consent has been signed, participants will be registered into the study database. The study database will assign a participant's PID upon completion of the registration process.

#### Randomization:

Participants will be assigned a randomization number once the following has been accomplished: eligibility has been verified, eligibility has been confirmed by the study PI, and eligibility CRF has been entered into the study database.

Patients will be stratified based on severity of disease as measured by PASI scores<12 (mild/moderate) or >=12 (Severe) at screening. Within each stratum, patients will be randomized at 1: 1 ratio to the two treatment arms using permuted block randomization with varying block sizes. Randomization codes will be shared to the study pharmacist at the initiation of the trial. The randomization will be performed by the statistician who will alert the pharmacy in coordination with the study coordinator.

#### Screening/Registration/Randomization into Study Databases

Appropriate CRFs must be completed for any participant who signs an informed consent. If a consented participant is a screen failure and deemed ineligible, the following CRFs must be completed: 1) the Screening CRF; 2) the Registration CRF with the eligibility box checked "no", 3) the Inclusion and Exclusion CRFs showing why the participant is ineligible, 4) the Off-Study CRF, 5) the Adverse Event CRF, 6) the Concomitant Medication CRF and 7) the Verification CRF. If no Adverse Event and/or Concomitant Medications were assessed by the time the participant is deemed ineligible, the "NONE" box will be checked to complete both CRFs. All participants who sign an informed consent must formally go off study. All participant registration information will

be entered into study database. If a participant experiences a serious adverse event during the screening process, an SAE form must be completed.

#### Blinding and Unblinding Method

- Patients and all clinical evaluators will be blinded to treatment assignment.
- The Statistician and the Study Pharmacist at the participating sites will not be blinded to treatment assignment.
- Study assignments will be unblinded to the Study Investigators and Coordinators after all of the data are collected, the study database has been locked, and analyses are completed.
- Emergency unblinding will occur if the participant's physician deems that unblinding is necessary, such as in the case of unacceptable toxicity thought to be related to the study agent or progressive disease.
- The Independent Medical Monitor will also be blinded unless unblinding is warranted (if the participant's physician deems that unblinding is necessary, or after all of the data are collected and the study database has been locked).
- The date and reason for breaking the blind must be documented in the study database.

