### **8. Study Intervention Discontinuation and Participant Discontinuation/Withdrawal**

#### **8.1 Discontinuation of Study Intervention**

Subjects will be withdrawn from study treatment permanently for the following reasons:

1. Development of any hypersensitivity phenomena that may be related to the study medication.
2. Excessive nausea making continuation of participation in the study impossible.
3. Development of any intercurrent illness or medical need to take a medication such that exclusion criteria apply.
4. Occurrence of pregnancy in a female subject.
5. If any clinical adverse event (AE), laboratory abnormality, or other medical condition or situation occurs such that continued participation in the study would not be in the best interest of the participant
6. Disease progression which requires discontinuation of the study intervention
7. If the participant meets an exclusion criterion (either newly developed or not previously recognized) that precludes further study participation

Subjects will be referred for appropriate medical care for any adverse effects.

Subjects will continue to be followed for assessment of disease severity until the 20-week period is over.

Discontinuation of treatment does not mean discontinuation from the study, and remaining study procedures (assessments of disease severity) will be completed as indicated by the study protocol.

If a clinically significant finding is identified (including, but not limited to changes from baseline) after enrollment, the investigator or qualified designee will determine if any change in participant management is needed. Any new clinically relevant finding will be reported as an adverse event (AE).

**Criteria for interrupting the study:** We will have a study monitoring committee (SMC) consisting of the study PI, the medical monitor and 1 investigator not directly involved in the conduct of this study. This committee will review all Grade 3 or 4 events, and all SAEs in real time. We will pause enrollment of new participants if there is 1 or more Serious Adverse Events that are at least possibly related to study drug, or 2 or more Grade 3 or 4 events at least possibly related to study drug. The enrollment of participants will not resume until the SMC reviews the adverse events and agrees unanimously to resume enrollment.

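### Section 7.11 offers progressive disease as an example ground for emergency unblinding, although worsening psoriasis is a poor result on the rated primary endpoint and drug can be stopped without the code

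*Combined protocol and SAP*

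**What the plan says.** The blinding rules are in section 7.11 under Blinding and Unblinding Method.

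- **Default.** "Patients and all clinical evaluators will be blinded to treatment assignment". No exception is attached.
- **Investigators and coordinators.** They learn assignments only once data collection, database lock and the analyses are complete. No emergency exception is attached here either.
- **Medical Monitor.** "The Independent Medical Monitor will also be blinded unless unblinding is warranted"; a judgement of necessity by the participant's physician is one of the stated warrants. This is the only blinded role with an express emergency exception.
- **Emergency break.** It rests on the judgement of the participant's physician, with two examples: "such as in the case of unacceptable toxicity thought to be related to the study agent or progressive disease". Progressive disease is not defined.
- **Record.** "The date and reason for breaking the blind must be documented in the study database". The recipient is not listed.

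Progression is also dealt with elsewhere. Section 7.9 ends treatment for "Disease progression requiring intervention", and section 8.1 lists "Disease progression which requires discontinuation of the study intervention". Neither calls for the code. Section 8.1 adds that "Discontinuation of treatment does not mean discontinuation from the study" and that "Subjects will continue to be followed for assessment of disease severity until the 20-week period is over".

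Sections 12.1 and 12.4.1 make percent PASI reduction from baseline to week 16 the primary measure, analysed by intention to treat, with last value carried forward only where the week 16 score is missing.

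**The concern.** In this trial, progressive disease means worsening of the condition that the primary endpoint scores. A rule that offers it as a reason to open the code ties loss of blinding to outcome: the subjects most exposed to a break are those doing badly, and if the drug works they would sit mainly on placebo.

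PASI and IGA are judged by a rater; DLQI and itch are reported by the subject. If either learns the assignment after a break, later scores can be coloured by it, and those scores still count. Scoring runs to week 20, and an observed week 16 value enters the intention-to-treat analysis. Keeping that value is ordinary good practice and is not the problem. The problem is that the plan invites an outcome-related break which it does not need, and does not restate the evaluator's blind once one has happened.

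**Working it through.** **1. Is the ground needed?** Set the provisions side by side.

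| Situation | What the plan already does | Code needed? |
|---|---|---|
| Psoriasis worsens, drug should stop | 7.9 and 8.1 stop drug; 8.1 keeps scoring | No |
| Rescue depends on whether rimegepant is on board | Physician's judgement of necessity in 7.11 | Possibly |

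An example of the second row is rescue with cyclosporine, which section 7.8 lists as both a P-gp and a BCRP inhibitor. Section 2.2 gives a half-life of 11 hours, so five half-lives are 5 × 11 = 55 hours. The need for the code is real but brief, and the physician's general discretion covers it without naming progression.

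**2. Who may receive the code?** Three bullets settle the default for patients and evaluators, investigators and coordinators, and the Monitor. The emergency bullet names a requester but no recipient. If the participant's physician is a study investigator, that bullet conflicts with the rule that investigators wait until after the analyses. If the physician is outside the study, nothing tells him or her to keep the assignment from the subject or evaluator.

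**3. The plan's own figure.** Inputs from section 12.2: 15 per arm, effect size 1.06, SD 20 points, two-sample t-test, two-sided 0.05. Exact noncentral-t power is 80.0%, so the stated 80% reproduces. The target difference is 1.06 × 20 = 21.2 points. No sample size or power figure in the plan changes because of this point.

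**4. Illustrative size.** The documents give neither a number of breaks nor a rating shift. Assume that the k lowest-scoring placebo subjects are each mis-scored by b points of percent PASI reduction.

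- Standard error of the arm difference = 20 × √(2/15) = 7.30 points.
- Shift in the arm difference = k × b / 15.
- Rejection rates: 200,000 simulated trials per case, normal data, 15 per arm, SD 20.

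| k, b | Shift (points) | Shift / SE | Share of 21.2 | Power, scored worse | Power, scored better |
|---|---|---|---|---|---|
| none | 0 | 0 | 0 | 80.0% | 80.0% |
| 1, 10 | 0.67 | 0.09 | 3% | 80.5% | 79.1% |
| 1, 20 | 1.33 | 0.18 | 6% | 80.7% | 77.5% |
| 2, 20 | 2.67 | 0.37 | 13% | 82.7% | 74.1% |
| 3, 20 | 4.00 | 0.55 | 19% | 85.0% | 69.8% |

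Scoring known placebo subjects worse enlarges the apparent effect; scoring them better shrinks it.

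With no true difference:

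| k, b | Favours rimegepant, scored worse | Favours rimegepant, scored better | Two-sided, scored worse | Two-sided, scored better |
|---|---|---|---|---|
| none | 2.5% | 2.5% | 4.9% | 4.9% |
| 1, 10 | 2.6% | 2.3% | 4.3% | 5.7% |
| 1, 20 | 2.6% | 2.0% | 3.7% | 6.6% |
| 2, 20 | 3.1% | 1.6% | 3.6% | 9.0% |
| 3, 20 | 3.9% | 1.1% | 4.2% | 12.0% |

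The two-sided excess in the last column consists of results favouring placebo.

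**The case against.** **The section is not silent on recipients.** A reader might infer that it leaves open who may receive a broken code. The text does not support that. Evaluators and patients are blinded without exception, investigators and coordinators wait until after the analyses, and only the Monitor has an emergency exception. The ordinary reading is that evaluators stay blinded. This stands. What remains is that the physician's receipt is implied and the evaluator's blind after a break is not restated. Taken alone, that would be missing detail.

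**Physician and rater may be different people.** Section 7.11 names the participant's physician apart from evaluators and investigators, and section 13.1.1 refers to consulting the subject's physician, which leans that way. It is not conclusive, and a physician outside the study is still under no instruction about passing on the assignment.

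**The break is already limited to emergencies judged necessary.** True: progression is an example under that test and not an automatic trigger. But naming it signals that worsening may suffice, when the plan has a route that keeps the blind.

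**The fix still permits a break for rescue.** Also true, and intended. Progression can create a care need; the need should be the ground, not the worsening itself.

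**The magnitude is invented.** The values of k and b are assumptions, and all altered subjects were placed on placebo, although breaks could also occur on rimegepant. The larger shifts require three of 15 subjects to be unblinded, disclosure to a rater or subject against the default rule, and a 20-point misrating of each. This stands, and it caps the severity.

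**Conclusion.** The point holds as a minor one: a cheap improvement, not an error that invalidates the trial. The plan expressly permits unblinding on a ground related to the primary outcome, already has a blind-preserving way to stop drug for that reason, and does not reconcile the emergency break with its own rules on who stays blinded.

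The likely effect is small and its direction unknown. Bias arises only if a break occurs and the rater or subject then learns the assignment. Under the assumed cases, one break leaves power between 77.5% and 80.7% and moves false positives favouring rimegepant from 2.5% to no more than 2.6%. Three breaks with 20-point misratings would matter more, but nothing in the documents makes that number likely.

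A reader might go further and infer that the primary result would be biased, or that scores taken after a break should be dropped. Neither follows. The documents do not show that an evaluator would receive the code, and retaining observed week 16 scores is what intention to treat requires.

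**What to change.** In section 7.11:

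1. Remove progressive disease from the example grounds, and limit emergency unblinding to cases where knowing the assignment changes immediate care. Worsening psoriasis is then handled by stopping drug under 7.9 and 8.1 with the blind intact, and a genuine rescue need stays covered.
2. State that the code goes only to the physician who needs it, that the PASI/IGA evaluator remains blinded and, where care allows, so does the subject. Reconcile this with the rule for investigators and coordinators.
3. Record the recipient beside the date and reason.

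The cost is two or three sentences and one data item, with no additional evaluator or subjects. The downside is that a physician who wants the code for worsening psoriasis must give a care-based reason.

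No sensitivity analysis need be required. One using the last score before the break would also remove the effects of stopping drug and of rescue, so it would not isolate rating bias.
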